5.0 Study Design and Statistical Analysis Plan

5.1 *Describe the basic study design/approach (e.g., qualitative study using five focus groups of first year students to describe assimilation into the university community; randomized controlled trial of a behavioral change intervention to increase dietary intake of whole grains; pre- post-test evaluation of new pedagogical techniques to improve adult literacy):*

In a one-session study, participants will complete assessments and purchase tobacco products in a hypothetical ETM. All participants will complete four ETM conditions, all of which include five trials assessing different prices of their preferred cigarette. In each

20-008 Effects of Cigarette and E-cigarette flavors on Substitutability in the Experimental Tobacco Marketplace

ETM condition, participants will purchase tobacco/nicotine products for a 7-day period. Unventilated and ventilated cigarettes, as well as a range of other products (i.e., lozenges, snus, gums, and dip), will be always available. Availability of e-cigarettes will vary according to the following conditions:

- A) Nicotine restricted and flavor restricted
- B) Nicotine unrestricted and flavor restricted
- C) Nicotine restricted and flavor unrestricted
- D) Nicotine unrestricted and flavor unrestricted

Participants will be exposed to these restriction conditions across purchasing scenarios in a counterbalanced order.

5.2 *Describe corresponding data analysis plan/approach (e.g., content analysis of focus group transcripts; descriptive analysis followed by linear regression modeling; nonparametric analysis of pre- and post-test measures):*

The analysis of each group will assess whether substitutability occurs as a function of different e-cigarette conditions. The relationship between consumption and condition will be modeled according to:

$$y_{ij} = \mu + \alpha_i + \tau_j + \varepsilon_{ij},$$

where y_{ij} represents the average log consumption for the i th e-cigarette restriction and the j th subject, α_i is the effect of the i th condition on log consumption, τ_j is the effect of the j th subject, ε_{ij} is the error term, $i=1, 2, 3, 4$ and $j=1, \dots, n$.

Additionally, all the groups will be compared to assess whether substitutability occurs as a function of different e-cigarette conditions. The relationship between consumption and condition will be modeled according to:

$$y_{ijk} = \mu + \alpha_i * b_j + \tau_k + \varepsilon_{ijk},$$

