where y_{ijk} represents the average log consumption by condition for the i th e-cigarette restriction, in the j th smoking status and the k th subject, α_i is the effect of the i th condition on log consumption, b_j is the effect of the j th group on log consumption τ_k is the effect of the k th subject, ε_{ijk} is the error term, $i=1, 2, 3, 4$, $j=1, 2, 3, 4$ and $k=1, \dots, n$.

Additional analyses might be conducted.

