8.0 Procedures Involved

8.1 Describe and explain the study design:

This study uses a mixed design (within-subject repeated measures and between-group). In a one-session survey, participants will complete assessments and purchase tobacco products in a hypothetical ETM. All participants will complete four ETM conditions, all of which include approximately five trials assessing different prices of their preferred

20-008 Effects of Cigarette and E-cigarette flavors on Substitutability in the Experimental Tobacco Marketplace

cigarette. In each ETM condition, participants will purchase tobacco/nicotine products for a 7-day period. Unventilated and ventilated cigarettes, as well as a range of other products (e.g., lozenges, snus, gums, and dip), will always be available. Availability of e-cigarettes will vary according to the experimental conditions:

- A) Nicotine restricted and flavor restricted
- B) Nicotine unrestricted and flavor restricted
- C) Nicotine restricted and flavor unrestricted
- D) Nicotine unrestricted and flavor unrestricted

Participants will be exposed to these conditions across purchasing scenarios in a counterbalanced order.

We will assess these measures in each of four smoker subtypes: unventilated menthol smokers, ventilated menthol smokers, unventilated non-menthol smokers, ventilated non-menthol smokers. For this purpose, ventilated and unventilated cigarettes will be defined as $\geq 20\%$ and $<10\%$ filter ventilation, respectively.

Every participant will complete questionnaires on a computer, tablet or cell phone.

8.2 *Provide a description of:*

- *All research procedures being performed*
- *If the study has more than one procedure, session, and/or subject population, describe each procedure, session, and/or study population separately. For complex studies, you are encouraged to include a figure or chart.*

Participants will complete a one session study including consent and behavioral tasks (ETM and smoking-related assessments).

A Qualtrics survey will administer:

1) the electronic informed consent;

Participants will read through the informed consent and consent will be implied with submission of the assessment at the end of the survey.

2) smoking-related assessments

a) timeline follow back, to assess previous month recent smoking, e-cigarette use and consumption of nicotine products, and to determine ETM budget

b) tobacco use history, exposure and preferences questions;

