14.0 Number of Subjects

14.1 Indicate the total number of subjects to be enrolled and how this number was determined (e.g., sample size calculation [show], number of available subjects in a finite pool, number of tests funding award would allow):

In this experiment, we request 268 participants for all four groups which will allow detection of effect size $f=0.24$ with 90% power using alpha =0.05 type I error rate and a within subject correlation of 0.5. According to Cohen's 1988 conventions, this is a medium effect size ($f=0.24$). This calculation was done using G*Power assuming a repeated measures ANOVA testing a within-between subject effect for the 4 conditions (e-cigarette flavor and nicotine restrictions).

Additionally, including all four groups together will provide more than sufficient power assuming a repeated measures ANOVA testing a within-between subject effect for 4 groups (between-factor; smoking preferences) and 4 conditions (within-subject; e-cigarette restriction).

14.2 If this is a multi-site study, indicate the number of subjects to be enrolled at this site and the total to be enrolled from all sites:

N/A

14.3 If applicable, indicate the number of potential subjects you expect to screen for enrollment, and the number of subjects you will need to complete the research procedures:

As stated previously, the survey will be conducted using the IPSOS web-enabled KnowledgePanel®, a probability-based panel designed to be representative of the U.S. population. We anticipate screening around 3,250 participants in order to complete a total of 268 participants.

14.4 If the study has more than one procedure, indicate the total number of subjects to undergo each procedure separately:

All participants will undergo one entire study session unless they withdraw consent.

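### Section 5.2 models four repeated conditions with one common error term and names no sphericity correction or covariance structure

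*Combined protocol and SAP*

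**What the plan says.** Every participant completes all the restriction conditions: "All participants will complete four ETM conditions, all of which include five trials assessing different prices of their preferred" cigarette (section 5.1). The four conditions cross e-cigarette nicotine (restricted or not) with e-cigarette flavor (restricted or not), in counterbalanced order.

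Section 5.2 gives two models. The first, fitted within each smoker group, has an outcome that "represents the average log consumption for the i th e-cigarette restriction and the j th subject", so each participant contributes four values. Its terms are condition, subject and one residual ("ε_{ij} is the error term"). The second covers all groups and combines condition with smoker group, again with one subject term ("τ_k is the effect of the k th subject") and one residual ("ε_{ijk} is the error term"). The groups are "unventilated menthol smokers, ventilated menthol smokers, unventilated non-menthol smokers, ventilated non-menthol smokers".

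Section 5.2 gives no residual distribution or covariance and does not say whether subject is fixed or random. It names no sphericity correction, robust variance or multivariate test, and defines no contrasts or confidence intervals. It closes by leaving room for further, unspecified analyses. Section 14.1 bases the sample size on a repeated measures ANOVA with "a within subject correlation of 0.5" and mentions no nonsphericity factor.

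**The concern.** With one additive subject term and one residual variance, the condition and group-by-condition F tests hold their level only under sphericity, that is, if the difference between any two conditions has the same variance for every pair.

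In a 2x2 design this means that participants must vary equally in their flavor effect, their nicotine effect and the interaction, and that these three must be uncorrelated. Nothing in the plan supports that. Some pairs of conditions share a flavor or nicotine level and others share neither, and counterbalancing the order does not change this.

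Two things are at stake. Omnibus tests would reject too often. Contrasts matter more: section 2.2 expects the least substitution when both features are restricted, and a three-degree-of-freedom test cannot answer that alone. If contrasts are drawn from the written model, they inherit a pooled error that may be too small or too large for the contrast in question.

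**Working it through.** **Inputs.** From 14.1: N = 268, f = 0.24, alpha = 0.05, correlation rho = 0.5. From 5.1 and 8.1: m = 4 conditions, k = 4 groups. Assumed: equal groups (268/4 = 67), normal data, and every covariance pattern below.

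**The plan's own figure.** Power uses the noncentral F with lambda = f² × N × m × epsilon / (1 − rho). For one group of 67 at epsilon = 1, lambda = 0.0576 × 67 × 4 / 0.5 = 30.87 on 3 and 198 df, giving power 0.998. On the stated inputs, 90% power needs 33 in one group (132 over four) or 46 in total for the 4x4 interaction. So 268 is not reproduced and exceeds what its inputs require. That is a separate matter and does not affect this point.

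**From covariance to epsilon.** With unit variances, write r_F for the correlation of pairs sharing a flavor level, r_N for pairs sharing a nicotine level and r_0 for pairs sharing neither. The normalized contrast variances are:

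- flavor: v_F = 1 + r_F − r_N − r_0
- nicotine: v_N = 1 + r_N − r_F − r_0
- interaction: v_I = 1 + r_0 − r_F − r_N

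The pooled error estimates their mean, v. Then epsilon = (v_F + v_N + v_I)² / [3(v_F² + v_N² + v_I²)], and a contrast's true-to-pooled standard error ratio is √(v_F/v) or √(v_N/v). Example, r_F = 0.8 and the others 0.3: the variances are 1.2, 0.2 and 0.2, and v = 0.533. Epsilon = 2.56/4.56 = 0.56, with ratios √(1.2/0.533) = 1.50 and √(0.2/0.533) = 0.61.

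**Simulated type I error (%), uncorrected, 67 per group.** The two contrast columns use the pooled error.

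| r_F / r_N / r_0 | epsilon | SE ratio, flavor / nicotine | condition | group x condition | flavor | nicotine |
|---|---|---|---|---|---|---|
| 0.5 / 0.5 / 0.5 | 1 | 1.00 / 1.00 | about 5 | about 5 | about 5 | about 5 |
| 0.6 / 0.45 / 0.45 | 0.93 | 1.18 / 0.89 | 5.4 | 5.5 | 9.7 | 2.8 |
| 0.7 / 0.4 / 0.4 | 0.76 | 1.34 / 0.77 | 6.4 | 7.0 | 14.2 | 1.2 |
| 0.8 / 0.3 / 0.3 | 0.56 | 1.50 / 0.61 | 7.8 | 9.2 | 19.1 | 0.17 |
| 0.6 / 0.6 / 0.3 | 0.76 | 1.18 / 1.18 | 6.6 | about 7 | 9.7 | 9.8 |

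Further non-spherical patterns, with epsilon 0.86 to 0.57, gave 5.6-8.0% for the condition test and 6.1-9.1% for group by condition. The approximate ceiling at epsilon = 1/3, the lowest value possible with four conditions, is 10.8% and 13.1%. Greenhouse-Geisser returned 4.6-5.2% in every pattern of that set. The flavor contrast on its own subject-level error gave 4.7-5.0%.

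**Equal correlations are not the condition.** With correlations from 0.33 to 0.61 but equal variances of all pairwise differences, epsilon is 1 and type I error is 4.8-5.0%. With all correlations 0.5 but SDs of 1, 1, 1 and 2, epsilon is 0.667 and type I error is 6.9-7.8%.

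**Both restricted versus the other three.** This contrast loads 2/3 on each of the three normalized contrasts. Its variance is therefore (4/9)(v_F + v_N + v_I) = (4/3)v, and its squared length is 1 + 3/9 = 4/3. The ratio is exactly 1.00 in every row of the table. That depends on equal variances. If the both-restricted condition had SD 2 and the others SD 1 (all correlations 0.5), the contrast variance is 4 + 6/9 − 2 = 2.667, or 2.0 per unit squared length, against a pooled error of (7 − 16/4)/3 = 1, and the ratio is √2 = 1.41.

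**Power after correction**, n = 67, f = 0.24, both df multiplied by epsilon:

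- 0.75: lambda 23.16, power 0.992
- 0.60: lambda 18.52, power 0.978
- 0.50: lambda 15.44, power about 0.96
- 1/3: lambda 10.29, power 0.885

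**The case against.** The best defense is that the plan is silent rather than committed to an error. It never states independent, identically distributed residuals or an uncorrected F test, and a Greenhouse-Geisser correction is compatible with a repeated measures ANOVA. A reader might infer that the planned tests will be wrong; the documents support only that they are not protected. That still leaves a choice affecting the error rate to be made after the data are seen.

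The contrast figures also describe an analysis that 5.2 does not define. This stands, so they are conditional on contrasts being tested against the pooled error.

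Other stronger readings also go too far:

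- **One restriction would be favored over the other.** The opposite-direction result needs an asymmetric covariance, in which sharing one feature matters more than sharing the other. Under the symmetric pattern both contrasts are inflated alike. If pairs sharing a nicotine level correlate more, the roles reverse. The documents do not say which applies.
- **The two restrictions could be ranked wrongly.** Section 16.3 withdraws anyone who stops before submitting. If every completer supplies all four values, condition means and contrasts do not depend on the assumed error covariance. Only standard errors and p-values change.
- **The test closest to the hypothesis is compromised.** The both-restricted contrast is undistorted under the equal-variance patterns.

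**Conclusion.** The point holds: the written models are safe only under sphericity, the design does not assure it, and no safeguard is stated. The omnibus effect is modest to moderate, within the ranges tabulated above. Pooled-error contrasts are more exposed: even at epsilon 0.93, where the omnibus tests look sound, the flavor contrast's error rate nearly doubles in the asymmetric pattern.

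All these magnitudes rest on assumed covariances, equal groups and normal data. Which contrast is affected, and in which direction, cannot be determined from the documents. A reader might also infer a threat to the sample size; the power figures do not support that. This is a cheap improvement, not a flaw that undermines the study.

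**What to change.** In section 5.2:

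- For the omnibus condition and group-by-condition tests, prespecify either a Greenhouse-Geisser correction or a mixed model with an unstructured 4x4 within-subject covariance and Kenward-Roger degrees of freedom.
- Define the one-degree-of-freedom contrasts that answer the hypothesis. Test each on the participant-level contrast score, with its own standard error, and use the same standard error for any interval reported.

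The cost is wording and slightly fewer error degrees of freedom. No participants need to be added: corrected power in a group of 67 is about 99% at epsilon 0.76 and about 96% at 0.5, and falls to about 89% only at the lower bound of 1/3.

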2.0 Objectives

2.1 *Describe the purpose, specific aims, or objectives of this study:*

Purpose: To examine the effects of filter ventilation and e-cigarette restrictions (on flavor and nicotine concentration) on cigarette demand and the corresponding degree to which e-cigarettes and other non-combustible tobacco products substitute for cigarettes.

2.2 State the hypotheses to be tested:

This study is designed to better understand the effect of possible e-cigarette restrictions. We hypothesize that e-cigarette restrictions will decrease substitution for e-cigarettes, with the smallest degree of substitution when both flavors and nicotine concentration are restricted.

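### The analysis plan names no test for its own hypothesis: the flavor-by-nicotine design enters only as a four-level condition factor, and only multi-df F tests are powered

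*Combined protocol and SAP*

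**What the plan says.** Section 2.2 gives the hypothesis in two parts. The first is direction: "We hypothesize that e-cigarette restrictions will decrease substitution for e-cigarettes". The second is ordering: "with the smallest degree of substitution when both flavors and nicotine concentration are restricted".

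Sections 5.1 and 8.2 set out four within-subject conditions: A (both restricted), B (flavor only), C (nicotine only) and D (neither). Sections 1.0 and 3.1 form four smoker groups from ventilation by menthol.

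Section 5.2 gives two models for mean log consumption:
- Within a group, there is one condition term with four levels, which "is the effect of the i th condition on log consumption". The stated purpose is: "The analysis of each group will assess whether substitutability occurs as a function of different e-cigarette conditions".
- Across groups, that term is crossed with a four-level group term, where "b_j is the effect of the j th group on log consumption".

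The section names no flavor, nicotine or flavor-by-nicotine effect, no comparison of A with the others, no ventilation or menthol contrast and no multiplicity rule. It ends: "Additional analyses might be conducted".

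Section 14.1 bases power on repeated-measures ANOVA, first "testing a within-between subject effect for the 4 conditions" and then "testing a within-between subject effect for 4 groups (between-factor; smoking preferences) and 4 conditions (within-subject; e-cigarette restriction" factor. It uses f = 0.24, alpha 0.05, 90% power, within-subject correlation 0.5 and N = 268.

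**The concern.** The design is factorial and the hypothesis is ordered, but the analysis treats the conditions as four unordered labels. A significant 3-df or 9-df F says that not all cell means are equal. It does not say which restriction is responsible, or whether restricting both does more than restricting one. Section 2.2 fixes the prediction in advance, but the form of the test, the comparators and the error control stay open until the data are in hand.

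This matters because section 3.3 expects the results to inform tobacco control policy. Whether two restrictions together do more than one is the question a 2x2 design is built to answer.

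A smaller, parallel gap concerns the smoker groups. The primary objective in section 1.0 names filter ventilation, yet the group factor merges ventilation with menthol and no contrast separates them.

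**Working it through.** **1. The plan's own figure.** For the 4 x 4 within-between test, take λ = f²·N·m/(1−ρ) with m = 4 and ρ = 0.5, on 9 and 3(N−4) df. At f = 0.24 and N = 46, λ = 0.0576 × 46 × 4/0.5 = 21.2 and power is 0.900. At N = 268, λ = 123.5 and power exceeds 0.999. So 268 does not follow from the stated inputs. That is a separate matter, and nothing below depends on it.

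**2. Is power lost at the planned effect size?** Assume sphericity and 67 per group (268/4; equal allocation is not stated).
- 3-df test in one group of 67: λ = 0.0576 × 67 × 4/0.5 = 30.9, on 3 and 198 df; power 0.998.
- 3-df test at N = 268: λ = 123.5, on 3 and 792 df; power 1.000.
- 9-df test at N = 268: above 0.999.

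So there is no practical loss at f = 0.24.

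**3. Where a single-df contrast does gain.** A flavor effect of d SD puts the four means at ±d/2, so f = d/2 and λ = N·4·(d/2)²/0.5. For d = 0.14 (f = 0.07), λ = 268 × 4 × 0.0049/0.5 = 10.51. Power is 0.90 with 1 df (0.84 at alpha 0.025) and 0.78 with 3 df. This effect is under a third of the planned f, and the 0.14 is an assumption, not a figure from the protocol.

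**4. What a significant F leaves undecided.** I simulated condition means with error variance 1 − 0.5 = 0.5 (SD 1), N = 268 and 792 error df, with 200,000 runs per pattern. Here 0.24 SD is the size of a restriction effect. For a flavor-only effect it equals f = 0.12, so it is not the protocol's f = 0.24.

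| True pattern, 0.24 SD | F rejects | F rejects and A has the lowest mean | A below B, C and D, each at two-sided 0.05 |
|---|---|---|---|
| Additive, A < B = C < D | 1.000 | 1.000 | 0.955 |
| Flavor only, A = B < C = D | 0.999 | 0.500 | 0.025 |
| Nicotine only, A = C < B = D | 0.999 | 0.498 | 0.025 |
| A = B = C < D | 0.989 | 0.330 | 0.005 |
| Additive, reversed | 1.000 | 0 | 0 |

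In rows 2 to 4 it is false that A alone is smallest. The 0.50 arises because two conditions tie for lowest and chance picks between them. The 0.025 is the chance that A falls significantly below the condition it is tied with.

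**5. Cost of the stricter rule.** With additive effects of 0.14 SD per restriction, A is significantly below all three others in 0.474 of studies, while the omnibus F rejects in 0.980.

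**The case against.** Several counterarguments stand in whole or part.

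- **No information is lost.** The four-level factors span the 2x2 effects, so every contrast can be estimated from the planned fit, and the fitted means show direction and rank. The gap is in specification.
- **Power.** A reader might infer that the omnibus tests are underpowered. Section 14.1's own f = 0.24 does not support that; the single-df advantage appears only for much smaller effects.
- **The 0.50 error rate.** A reader might take this as the plan's false-positive rate. It is not. The plan nowhere says that a significant F plus the lowest mean will count as proof, and the figure follows almost automatically from a tie. It shows what an unspecified reading could do.
- **Non-directional tests.** That F rejects equally under a reversed pattern is a weak complaint taken alone. A two-sided contrast does so too, judged by its p-value, and direction then comes from the sign of the estimate. What a contrast adds is that the sign belongs to one named effect.
- **The endpoint.** Section 4.1 ties substitutability to flavor and nicotine restrictions and to cigarette price, which points to the factors of interest. It still names no contrast.
- **The outcome comes first.** Section 3.1 defines substitution as a response to another product's price, whereas section 5.2 models mean log consumption with no product named and no price term. Contrasts on that outcome compare consumption levels, so the outcome must be named with them.
- **The subtype aim.** The four-level group factor does serve section 3.1's aim of seeing whether effects differ by subtype. Only the separate ventilation question lacks a contrast.

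Holm, two-sided testing and the ranking of the ventilation results are choices; other defensible sets exist, such as each restriction against D.

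**Conclusion.** The point holds as a gap between hypothesis and analysis. Followed as written, the plan tests whether the four conditions differ. It names no test of either restriction's own effect or of the both-restricted condition being smallest. It should be corrected before analysis, but it does not threaten the data or the design.

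Its size is best shown by the illustration: 0.50 against 0.025 when one restriction alone acts, and 0.33 against 0.005 when A, B and C are equal. This assumes SD 1, correlation 0.5, sphericity, N = 268 and a 0.24 SD effect. The documents do not support a claim of lost power at f = 0.24, nor a claim that the plan itself carries a 50% error rate.

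**What to change.** Revise section 5.2 as follows.

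1. Name the outcome: e-cigarette consumption, or the study's substitution measure, defined explicitly.
2. In the pooled model with a subject effect, code condition as flavor, nicotine and flavor x nicotine.
3. Name the flavor and nicotine effects as the primary contrasts, with a stated multiplicity rule. Holm at familywise 0.05 is one option.
4. Test the ordering claim by requiring A below B, A below C and A below D, each at two-sided 0.05. State how this test sits relative to the two primary contrasts.
5. Code group as ventilation, menthol and their interaction, and cross these with the condition effects. Report ventilation results as associations, because groups follow preferred cigarette and are not randomized.
6. Keep the omnibus and by-group tests as supporting analyses.

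The cost is SAP wording plus a decision on the outcome; sample size, data collection and software are unchanged. The downside is that the all-three rule is demanding for small effects: power is about 0.47 at 0.14 SD per restriction and about 0.95 at 0.24 SD, with N = 268.
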